9.3 POPULATIONS FOR ANALYSES

Patient-surrogate dyads will be the primary unit of analysis; all analyses will be intent to treat with all available data from all participants.

9.4 STATISTICAL ANALYSES

9.4.1 GENERAL APPROACH

The preliminary analysis will include summarizing variables with standard descriptive statistics and graphical displays or frequency tables. Distributional assumptions will be assessed and the data will be transformed as necessary. Clinic characteristics (e.g., rural-urban status) will be compared using χ^2 tests for categorical variables and t-tests for continuous variables. We will compare SPIRIT and usual care participants on baseline characteristics (e.g., age, race/ethnicity) to explore possible between-group differences using generalized estimating equation (GEE) methods, accounting for the observed correlation within the same cluster.^{90,91} In our previous work SPIRIT has no effect on patient mortality²⁰; however, we will compare survival time between SPIRIT and usual care using Cox proportional hazards models, adjusted for cluster effects. If imbalanced, we will consider adjustment for the group difference.

9.4.2 ANALYSIS OF THE PRIMARY ENDPOINT(S)

SPIRIT effectiveness on the preparedness outcomes: Dyad congruence and the composite outcome (binary variables) will be analyzed by fitting a generalized mixed effects model for each, where the binary outcome is modeled in terms of a logit link⁹⁰ with both a random intercept and random slope to control for variation within and between subjects and clusters. The model also includes the intervention SPIRIT, cluster size and their interaction. For patient DCS and surrogate DMC scores, we will replace the logit link by the identity link with an additional error term. These models will allow us to examine whether SPIRIT was superior to usual care in the primary outcomes at 2 weeks and whether the effect of SPIRIT varies by cluster size. The analysis will be adjusted for potential covariates, such as race/ethnicity, and rural-urban status, in the model, including interaction between treatment and race/ethnicity.

For Supplement Aims:

To account for small sample size, resampling methods will be used for all analyses and 95% bootstrap confidence intervals of the differences in outcome scores will be reported.

- 1) Aim 1. SPIRIT effects on the preparedness outcomes:** For testing the effect of the intervention on dyad congruence, a paired binary outcome (congruent or not congruent), McNemar's test will be used. In addition, a logistic regression model will be used to test for differences in post-intervention outcomes by groups after adjusting for potential covariates. The adjusted ratio of odds of congruence in the intervention group versus the control group will be evaluated and reported as an effect size estimate.
- 2) Aim 1. SPIRIT effects on care decisions:** Differences in proportion of decisions made (e.g. stopping dialysis, DNR order, and hospice enrollment etc.) at 6-month follow up or death of patient will be described across groups and used as effect size. We will also explore time to event analysis to assess the difference in rate of risks between the two groups using non-parametric and semiparametric methods.
- 3) Aim 2. Surrogate post-bereavement distress (HADS scores):** Differences in the HADS subscale scores between the intervention and control groups will be assed using t-tests. Because, we estimate a 50% rate of death during the study, the number for this analysis would be n=15. A standardized difference between groups will be used as an effect size estimate.
- 4) Aim 3. Relationships among patients' cognitive status, decision-making capacity and their ability to express end-of-life wishes:** For patients in the SPIRIT intervention arm (n=15), associations between patients' cognitive status (continuous), decision-making capacity (continuous) and their ability to express end-of-life wishes (categorical) will be analyzed using one-way analysis of variance (ANOVA). We will also explore ordinal logistic regression to obtain the proportional odds ratios defined by the odds of "expressing wishes very coherently" or

“expressing wishes somewhat coherently” versus the odds of “unable to express wishes coherently” for a unit increase in cognitive status or decision-making capacity.

Supplement cohort study:

As in the parent R01, we will use the Research Electronic Data Capture (REDCap) to create and update study participants’ data. During data entry, automated checks will be performed that will immediately flag problematic data (e.g., missing, out of range, inconsistent). Preliminary analyses will include summarizing variables with descriptive statistics and graphical displays. We will assess distributional assumptions of the outcomes and apply appropriate transformations to remedy any violations. Any differences in patient characteristics (e.g. age, sex, education level, household income) across groups will be adjusted when modeling the outcomes. As observed in the parent R01 (< 1% missing data), we expect very little missing data. Nonetheless, we plan to use restricted maximum likelihood (REML) method for estimating the repeated measures analysis to minimize the impact of missing data. This will make it possible to retain cases with partial data while making less restrictive assumptions about missing data patterns.

Aim 1. Compare the stability of patients’ goals-of-care preferences over time, from pre-outbreak to during-outbreak, by group and estimate effect by race: We will use mixed effects modeling to assess differences in patients’ goals of care over time, from pre- to post-lockdown time points. We will sequentially build a longitudinal model that will include time, treatment group and race as fixed effects; then 2-way interactions of time x group, time x race, treatment x race, and finally a 3-way interaction of time x group x race, if the sample size permits. We will select the most parsimonious model using Akaike information criterion (AIC) and Bayesian information criterion (BIC). We will use contrasts to test whether participants demonstrated significant change in goals-of-care preferences across different combinations of treatment and race.

Aim 2. Assess the stability in the three preparedness outcomes, from pre-outbreak to during-outbreak by group, and estimate race effect: We will perform analyses similar to those described in Aim 1. In addition, for non-normal outcomes (binary, count) a generalized mixed effects model will be used. Appropriate contrasts will be used to assess differences in the outcomes over time by treatment groups, race and groups x race.

Aim 3. Examining the associations of the COVID-19 Related Stress, sex, race/ethnicity, and other sociodemographic characteristics to the level of changes in the preparedness outcomes and patient’s goals-of-care preference stability: We will use analysis of covariance to assess the relationship between COVID-19 related stress and changes in outcomes from T2 to T3 and T3 to T4, after controlling for the corresponding baseline values of the outcomes (i.e., T2 and T3 respectively). Using similar methods, we will evaluate whether there are disparate effects of sex, race/ethnicity and other sociodemographic factors on outcome changes and goals-of-care preference stability from T2 to T3 and T3 to T4, respectively

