A new supplement study is a longitudinal cohort study leveraging the parent study. The objective is to assess the effect of the pandemic on the stability of end-of-life care preferences and on our key outcomes (dyad congruence on goals of care, patient decisional conflict, and surrogate decision-making confidence).

Aim 1. Compare the stability of patients' goals-of-care preferences over time, from pre-outbreak to during-outbreak, by group (SPIRIT vs control) and estimate effect by race (Blacks and Whites).

Aim 2. Assess the stability in the preparedness outcomes (dyad congruence, patient decisional conflict, and surrogate decision-making confidence) comparing pre-outbreak to during-outbreak by group, and estimate race effect.

Aim 3. Examine the associations of the COVID-19 Related Stress questionnaire, sex,

race/ethnicity, and other sociodemographic characteristics (e.g., education level, income) to change in the outcomes and the stability of patients' goals-of-care preferences after the COVID-19 outbreak.

Endpoints:

Primary Endpoints (Aim 1):

Dyad congruence on goals of care, patient decisional conflict, and surrogate decision-making confidence at 2 week post-intervention

Secondary Endpoints (Aim 3):

Surrogate HADS and PTSS scores at 3 months after the patient's death;

Exploratory (Aim 4):

EOL treatment intensity

Supplement Aim:

Dyad congruence on goals of care, patient decisional conflict, and surrogate decision-making confidence at 2-3 day post-intervention

Study Population:

400 patients and 400 surrogates of the patients participate as pairs (400 patient-surrogate dyads); adults (≥ 18 y); both genders; all race and ethnicity; ESRD/chronic dialysis population

For the supplement aims:

30 patients with ESRD + cognitive impairment, including early stages of dementia, who are not eligible for the parent study due to cognitive impairment, and 30 surrogates of the patients as pairs

Supplement cohort study:

~100 dyads who completed the baseline assessment and post-intervention assessment prior to the pandemic lockdown.

Phase:

Phase III effectiveness trial

For the supplement aims, NIH Stage 1 biobehavioral intervention research

**Description of
Sites/Facilities Enrolling
Participants:**

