Recruitment will occur over 24 months beginning at the end of Year 1. We are highly experienced in recruiting seriously ill ESRD patients and their surrogates for research. Consent rates in our previous studies have been consistent at approximately 84% despite the studies' focus on end-of-life, the requirement that both patient and surrogate participate, and long-term follow-up. We expect a similar if not higher consent rate because the study involves a shorter follow-up time and minimal data collection directly from patients and surrogates. Based on our previous studies,¹⁸⁻²⁰ we conservatively anticipate that 427 patients (20%) will be *eligible and willing* to participate. To reach 400 dyads, we expect to enroll 21-22 dyads per cluster on average. These clinics each accept 10-70 new patients each year (total 700 additional patients), and thus our recruitment goal is readily achievable.

To Maximize Participant Retention, strategies found effective in retaining dyads over 12 months (dropouts, 3.8%) in our efficacy trial²⁰ will be used: we will

- a) obtain two backup contacts from each member of the dyad in the event that we cannot reach them by telephone and mail
- b) make confirmation phone calls 2 days prior to each follow-up
- c) make monthly check-in calls
- d) send holiday cards
- e) assign the same data collector whenever possible
- f) compensate each member of the dyad with gift cards (\$15 at baseline, \$15 at 2 weeks for the preparedness outcome assessment; \$20 at 3 months for the post-bereavement outcome assessment). Consistent with a pragmatic trial, participants will not be compensated for participating in the intervention. The Emory Study Coordination Center will be responsible for disbursement.

For Supplement Aims:

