6.3 MEASURES TO MINIMIZE BIAS: RANDOMIZATION AND BLINDING

Clinics covered by the same care provider who will deliver SPIRIT sessions will be combined to one cluster to avoid risk of contamination; this results in clusters (4 in GA, 3 in NC, 8 in NM, 5 in PA and 8 in VA). Because the numbers of available patients substantially vary across the clusters, to minimize group imbalance clusters will be stratified to three sizes: small (patient census ≤ 52), medium (53-105), and large (≥ 106). We will randomize clusters to either SPIRIT or usual care plus delayed SPIRIT, with randomly permuted blocks (sizes of 2 and 4) within cluster size stratum nested in each state, using a pseudo-random-number generator, by the Study Coordination Center.

Before the study starts, the Study Coordination Center will inform the group assignment for each cluster to the site PIs, with a unique ID consisting of abbreviations for state and cluster size stratum. While the heterogeneity in minority race/ethnicity across clusters improves the study's generalizability, stratification or pairing clusters by race/ethnicity is not feasible because some clinics uniquely serve one race with no comparable clinics within state. Group imbalances on race/ethnicity and other potential confounding factors will be examined and adjusted for in the analyses. The cluster randomized design prevents blinding patient-surrogate dyads and dialysis care providers to group allocation. However, research staff assessing effectiveness outcomes will be blind to group assignment.

For Supplement Aims:

[name] (biostatistician/Co-I) will generate a randomization scheme using stratified (by race), permuted block randomization with block size 5, using a random-number generator. Dyads will be randomized with equal allocation (1:1) to SPIRIT or usual care. Due to the nature of the intervention, blinding dyads to their group allocation is impossible, but the research staff assessing outcomes will be blind. Immediately after the completion of the baseline assessment by phone, the data collector will open a sealed envelope to identify group assignment and schedule an intervention session to take place ~ 2 weeks hence for SPIRIT as well as a follow-up data collection session in the next 2-3 days.

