9.2 SAMPLE SIZE DETERMINATION

We have an adequate sample size to detect clinically meaningful differences between SPIRIT and usual care for our primary outcomes. Statistical power is based on a random effects models: a generalized linear mixed model for binary outcomes (e.g., dyad congruence) and a linear mixed model for continuous outcomes (e.g., patient decisional conflict).

We conducted a simulation study to estimate power with 2-sided significance level alpha=.05, corrected for anticipated dropout and potential intraclass correlations (ICCs) ranging .01-.04, based on ICCs observed in our prior work. To estimate the power more conservatively, we used the effect sizes observed at 2 months²⁰ rather than those at 2 weeks,¹⁸ which are larger (e.g., for the composite outcome, *OR*=1.8 at 2 months, *OR*=4.4 at 2 weeks). The overall power to detect clinically meaningful differences is excellent for the primary outcomes and good for the post-death outcomes.

Power for comparing SPIRIT and usual care with 19 clusters				
Aim 1	Percent or min. difference	OR or variance	ICC ^a	Estimated power
Dyad congruence	48%	OR =2.0	0.02 0.04	0.92 0.84
Patient DCS	d =0.24	0.23	0.01 0.10	0.98 0.81
Surrogate DMC	d =0.22	0.20	0.01 0.10	0.99 0.80
Composite outcome	47%	OR =2.0	0.02	0.93
Aim 3				
Anxiety	d =1.35	7.0	0.01 0.03	0.84 0.80
Depression	d =1.60	10.0	0.01 0.03	0.85 0.79
PTSS-10	d =4.75	90.0	0.01 0.03	0.85 0.78

^a observed ICCs in our prior work; *d*=1/2 *SD*.

DCS, decisional conflict scale; DMC, decision-making confidence.

For Supplement Aims:

Because this is a pilot study, prior estimates of effect sizes were not available; thus a traditional sample size calculation was not performed. Instead we focused on calculating the minimum effect size that can be detected with adequate power (>=80%). Based on preliminary calculations, we found that a sample size of 30 will achieve 80% power to detect an effect size (Cohen's *f*²) of 0.28 (moderate-high), attributable to the treatment group indicator using an F-test at a 5% significance level. We will use the estimates of effect sizes obtained from this study for sample size calculations in future larger studies.

Supplement cohort study:

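### Section 9.4.2 names no estimator, reference distribution or small-sample method for a cluster-randomised effect tested on 19 or 28 clusters; default Wald z tests would run at about 5-7% (continuous, REML) or 5-9% (binary).

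*Combined protocol and SAP*

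**What the plan says.** Section 6.3 makes the cluster the unit of allocation: "We will randomize clusters to either SPIRIT or usual care plus delayed SPIRIT". It lists the clusters by state: "this results in clusters (4 in GA, 3 in NC, 8 in NM, 5 in PA and 8 in VA". These sum to 4 + 3 + 8 + 5 + 8 = 28. The power table in section 9.2 is headed "Power for comparing SPIRIT and usual care with 19 clusters" and uses a "2-sided significance level alpha=.05". Section 5.5 fits the 19: "we expect to enroll 21-22 dyads per cluster on average" (400/19 is about 21; 400/28 is about 14).

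For the primary endpoints, section 9.4.2 states: "Dyad congruence and the composite outcome (binary variables) will be analyzed by fitting a generalized mixed effects model for each". The link is logit, with a random intercept and a random slope. DCS and DMC use the identity link. The fixed part holds SPIRIT, cluster size and their interaction, with adjustment for covariates that include rural-urban status.

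Nothing in sections 9.2 to 9.4.2 says, for the parent trial, whether the fit is ML or REML, what distribution the test statistic is referred to, or how degrees of freedom are counted. Two sentences look like an answer but belong elsewhere. The resampling sentence in 9.4.2 stands under the supplement aims (the 30-dyad dementia pilot), and REML is named only for the COVID-19 cohort supplement.

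**The concern.** SPIRIT varies only between clusters. However many dyads are enrolled, its standard error depends on a between-cluster variance estimated from 19 or 28 units. Referring the estimate to a normal distribution ignores the uncertainty in that variance. ML adds a downward bias in the variance, and each cluster-level covariate uses up another degree of freedom.

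With the plan silent, one analyst could report ML with Wald z and another REML with Kenward-Roger. On a borderline primary result they could reach different conclusions, and the first would be working above the stated 5%.

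**Working it through.** **1. Reproduce the stated power (DCS and DMC, ICC 0.10).** Inputs from sections 1.1 and 9.2: N = 400 dyads, K = 19, two-sided 5%; DCS difference 0.24, variance 0.23; DMC difference 0.22, variance 0.20. Near-equal arms are assumed.

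- m = 400/19 = 21.05; design effect = 1 + (m − 1) × 0.10 = 3.005.
- SE = sqrt(4 × variance × design effect / N).
- DCS: SE = sqrt(4 × 0.23 × 3.005/400) = 0.0831; 0.24/0.0831 = 2.887; power with z = Φ(2.887 − 1.960) = 0.823.
- DMC: SE = sqrt(4 × 0.20 × 3.005/400) = 0.0775; 0.22/0.0775 = 2.838; power with z = Φ(2.838 − 1.960) = 0.810.

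| Endpoint | Stated | z, N = 400 | z, N = 385 | t(17), N = 400 |
|---|---|---|---|---|
| DCS | 0.81 | 0.823 | 0.819 | 0.777 |
| DMC | 0.80 | 0.810 | 0.805 | 0.763 |

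N = 385 applies the 3.8% dropout quoted in section 5.5 from the earlier trial. The stated figures fit z and not t with K − 2 = 17 degrees of freedom. At ICC 0.01 both references give about 0.99, so that row does not discriminate. The dyad-congruence row (stated 0.92 and 0.84) does not reproduce with a simple design effect (0.82 and 0.72), so it says nothing either way.

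**2. Degrees of freedom for the planned model.** Intercept, SPIRIT, linear cluster size and its interaction are 4 parameters; with three size strata there are 6. That leaves 15 or 13 at K = 19, and 24 or 22 at K = 28, before rural-urban status is added. The figures 17 and 26 apply only to an unadjusted model.

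**3. Closed form: true size of |T| > 1.96 when T follows a t distribution.**

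| df | Size | Correct critical value |
|---|---|---|
| 17 | 6.7% | 2.110 |
| 15 | 6.9% | 2.131 |
| 13 | 7.2% | 2.160 |
| 26 | 6.1% | 2.056 |
| 22 | 6.3% | 2.074 |

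At 17 df a z-based interval is 1.96/2.110 = 0.93 of the proper width; at 13 df it is 1.96/2.160 = 0.91.

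**4. Simulation under the null.** Random-intercept models, 400 dyads, cluster-size coefficient of variation 0.5 (an assumption), run unadjusted, with three size strata, and with strata by SPIRIT. There were 4,000 runs per cell for the linear model and 2,000 for the logistic (base rate 48%, ML by quadrature). Ranges are over the three adjustments.

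| Model and test | ICC | 19 clusters | 28 clusters |
|---|---|---|---|
| Linear, REML, z | 0.01-0.04 | 5.5-6.8% | 5.0-6.3% |
| Linear, REML, z | 0.10 | 6.4-7.1% | 5.5-7.0% |
| Linear, ML, z | 0.01-0.10 | 6.7-11.5% | 5.7-9.1% |
| Logistic, ML, z | 0.02-0.04 | 6.1-9.2% | 6.0-7.7% |
| Logistic, ML, t(K − p) | 0.02-0.04 | 4.4-6.6% | 4.8-6.6% |

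Monte Carlo standard error is about 0.3-0.4 points (linear) and 0.5-0.7 points (logistic). A second simulation of the logistic model with z gave 5.9-8.7% at 19 clusters and 5.2-5.5% at 28 for the same ICCs. The rounded range of 5-9% covers both. The range 0.02-0.04 is the one in the power table's binary rows. At ICC 0.10, which the table uses only for DCS and DMC, the logistic model at 19 clusters gave 8.6-12.2% with z and 6.6-8.9% with t.

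**The case against.** The best answer is that the plan is silent, not wrong. No z test, cut-off of 1.96, ML fit or software is named, and an analyst who chose REML with Kenward-Roger would comply with section 9.4.2. A reader might infer that the tests do exceed 5% and that the intervals for every primary endpoint are too narrow. The documents do not support that. The match of the power figures to z is evidence about the section 9.2 calculation, whose details are not given, and only indirectly about the test to be used.

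Nor does the size of the problem reach every endpoint. Under REML with 28 clusters and ICC 0.01-0.02, the z test for DCS and DMC ran at 5.0-5.5%, which is negligible. The count of 28 comes from the section that describes the randomisation, so 19 may be the less relevant figure.

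It can also be said that the simulated models are simpler than the planned one. That is so: the random slope and individual-level covariates were left out because the text does not define them well enough to simulate.

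All of this makes the claim conditional. It does not remove the omission, since none of it supplies a method for the parent trial.

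**Conclusion.** The point holds as a gap in specification with a conditional consequence. For a cluster-level effect on 19 or 28 clusters, the parent-trial analysis names no estimator, reference distribution or small-sample method. If default Wald z tests are used, type I error would be about 5-7% for DCS and DMC under REML and about 5-9% for the binary endpoints at ICC 0.02-0.04. The upper ends come with 19 clusters and the cluster-level terms, and ML fitting takes the linear model higher still, to 11.5% at worst.

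These figures rest on random-intercept models, an assumed spread of cluster sizes, and ICCs taken from section 9.2. Its text gives "potential intraclass correlations (ICCs) ranging .01-.04, based on ICCs observed in our prior work", while its table goes to 0.10 for DCS and DMC. The failure of the binary power row to reproduce might be read as an error in the plan. It should not be: section 9.2 used a simulation whose inputs, such as any use of baseline data, are not stated.

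**What to change.** 1. **DCS and DMC:** fit by REML with Kenward-Roger degrees of freedom.
2. **Dyad congruence and composite:** name the estimator. Refer the SPIRIT test to a t distribution with between-cluster degrees of freedom counted for the full planned model: about 13-15 at 19 clusters with cluster size and its interaction, fewer with rural-urban status. Support it with a permutation test over the actual stratified cluster allocation, because a t reference alone may not hold 5% for a logistic model fitted by ML. State in advance which result decides.
3. **Cluster count:** reconcile 19 (section 9.2) with 28 (section 6.3).
4. **Power table:** recompute it with the same cluster count and reference distribution as the analysis.
5. **Scope:** sections 9.4.3 and 9.4.9 reuse the primary approach, so the wording should cover them.

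The cost is SAP text, software options and one re-run of the power simulation; no new data are needed. Stated power falls slightly. At 19 clusters and ICC 0.10, DCS and DMC go from 0.81 and 0.80 to about 0.78 and 0.76 with 17 df, and to 0.76 and 0.75 with 13. If 28 clusters is right and N stays at 400, the same calculation gives about 0.88 and 0.87 with 22-26 df. The effect on the binary rows cannot be given until the simulation behind them is re-run.

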8 STUDY ASSESSMENTS AND PROCEDURES

8.1 OUTCOME ASSESSMENTS

Collecting effectiveness outcome data will be centralized; research staff at the Study Coordinating Center will collect the data from patients and surrogates by phone. Telephone-based collection minimizes participants' travel burden. Centralized data collection maintains data collectors being blind to group assignment. The preparedness outcomes will be assessed at 2 weeks post-intervention, as in our R21 trial.¹⁸ We expect roughly 40% of study patients (~160) to die by the 9-month follow-up; deaths are readily identifiable through dialysis clinics and will trigger post-bereavement surveys with surrogates at 3 months and staggered CMS data collection. Post-bereavement assessment at 3 months is based on our efficacy data showing that distress symptoms sharply rose in both groups 2-weeks post-bereavement and then stabilized at 3 months.

Effectiveness Outcomes

Preparedness for end-of-life decision making (measured at baseline and 2 wks post-Session II):

- **Dyad congruence** will be assessed using the Goals-of-Care Tool,^{18,20} which includes two scenarios describing medical conditions commonly occurring in ESRD patients. In the first, the patient develops a severe complication and cannot speak for himself/herself; the medical team believed recovery unlikely and continuing life-sustaining treatment, including dialysis, would no longer be beneficial. In the second scenario, the patient develops advanced dementia. Each scenario has three response options: "The goals of care should focus on delaying my death, and thus I want to continue life-sustaining treatment", "The goals of care should focus on my comfort and peace, and thus I do not want life-sustaining treatment, including dialysis", and "I am not sure". Patients and surrogates complete this tool independently and their responses are then compared to determine dyad congruence -- either congruent in both scenarios or incongruent. If both members of the dyad endorse "I am not sure", they are considered incongruent.
- **Patient decisional conflict** will be measured using the 13-item Decisional Conflict Scale (DCS), a validated measure in the context of end-of-life decision making¹⁷; higher scores indicate greater difficulty in weighing benefits and burdens of life-sustaining treatments and decision making (range 1-5; Cronbach's $\alpha = 0.8 - .93^{17,18,20,72}$).

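### The primary mixed model in 9.4.2 is not estimable for its 2-week target: one follow-up value per dyad cannot support the subject-level effects, and no visit term is listed if both visits are modelled

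*Combined protocol and SAP*

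**What the plan says.** Section 9.4.2 models dyad congruence and the composite with a logit-link mixed model "with both a random intercept and random slope to control for variation within and between subjects and clusters". On fixed effects: "The model also includes the intervention SPIRIT, cluster size and their interaction". Further terms follow: "The analysis will be adjusted for potential covariates, such as race/ethnicity, and rural-urban status, in the model", together with a treatment by race/ethnicity interaction. For the DCS and the surrogate Decision Making Confidence (DMC) score, "we will replace the logit link by the identity link with an additional error term". The stated purpose is to examine "whether SPIRIT was superior to usual care in the primary outcomes at 2 weeks".

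Section 8.1 gives the measurement times: "Preparedness for end-of-life decision making (measured at baseline and 2 wks post-Session II". Section 9.3 makes the dyad the unit of analysis. Section 6.3 randomizes clusters, so treatment is constant within a cluster. Sections 9.4.3 and 9.4.9 reuse this approach for the bereavement and end-of-life treatment outcomes.

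Section 9.4.2 does not say which visits enter as outcomes, which variable the slope is on, or at which level each random effect sits. For the parent trial it names no visit term, no SPIRIT-by-visit term and no baseline outcome.

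**The concern.** Words about within-subject variation and a random slope describe a repeated-measures model. The listed fixed effects and the 2-week target describe a single-timepoint comparison. The two do not combine into one model. Either the subject-level random effects have no data behind them, or the SPIRIT coefficient is not the 2-week effect.

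All four primary hypotheses in 9.1 rest on this model. If it fails to converge, or converges to something other than the 2-week difference, the analyst must choose a replacement with the outcome data in hand. Prespecification is meant to prevent exactly that.

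**Working it through.** **Inputs.** From the 9.2 table: DCS difference 0.24 and variance v = 0.23; DMC difference 0.22 and variance 0.20; ICC 0.01 and 0.10; 19 clusters; two-sided 0.05. The 400 dyads are from the synopsis. Section 6.3 lists 4 + 3 + 8 + 5 + 8 = 28 clusters. Assumed, because the documents give no figure: equal allocation, between-visit correlation ρ from 0.3 to 0.7, and about 4% dropout (384 dyads) for the reproduction only.

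**1. The plan's own power.** For a single-timepoint comparison with a cluster effect, SE = √(4v[1 + (m−1)ICC]/N), with N = 384 and m = 384/19 = 20.2. For DCS at ICC 0.10, SE = 0.0837 and power is 0.82 (stated 0.81). At ICC 0.01 power is 0.99 (stated 0.98). DMC gives 0.99 and 0.81 (stated 0.99 and 0.80). The continuous rows therefore agree with a one-visit, cluster-intercept model.

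**2. One 2-week record per dyad.**
- Identity link: the dyad-intercept variance and the error variance enter only as their sum.
- Logit link: in simulated data the maximised log-likelihood was −270.902081 for a dyad SD of 0, 0.5, 1 and 2, while the fitted SPIRIT odds ratio was 1.73, 1.79, 1.94 and 2.47. The fit is the same and only the conditional scale moves.
- A subject-level slope has no within-subject variable. The cluster intercept is identified.

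**3. Both visits as outcomes: variance parameters.** A dyad intercept, slope, their covariance and a residual are 4 parameters. Two visits supply 3 moments (two variances and one covariance). A dyad intercept with a cluster intercept and a cluster slope on visit is identified.

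**4. Both visits as outcomes: what the SPIRIT term estimates.** With SPIRIT as a constant group indicator and no SPIRIT-by-visit term, generalized least squares gives the 2-week difference the weight (a − c)/(a + b − 2c). Here a and b are the baseline and 2-week variances and c is their covariance.
- Random intercept only, residual variance σ²: a = b and a − c = σ², so the weight is σ²/2σ² = 0.50.
- Uncorrelated dyad slope of variance s, visit coded 0/1: b = a + s, so the weight is 1/(2 + s/σ²). For s/σ² = 0.5, 1 and 2 this is 0.40, 0.33 and 0.25.
- Cluster slope on visit: a small simulation (20 clusters of 20 dyads, 25 replicates per setting) gave weights of about 0 to 0.33.
- Adding a visit main effect alone does not repair this. In the same simulation the random-intercept weight stayed at 0.46-0.53. SPIRIT-by-visit is the term that is needed.
- Logit link, true 2-week odds ratio 2: the SPIRIT term gave 1.37-1.38. With visit and SPIRIT-by-visit added, the log odds ratio was 0.67 against a true 0.69.

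**5. Size in the one-half case (DCS).** The effect is 0.24/2 = 0.12. With K clusters of m = 400/K dyads:
- 2-week comparison: Var = 4v[ICC + (1−ICC)/m]/K
- two-visit average: Var = 4v[ICC + ((ρ−ICC) + (1−ρ)/2)/m]/K

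| ICC | K | Power, 2-week effect 0.24 | Power, averaged effect 0.12 (ρ 0.7 to 0.3) |
|---|---|---|---|
| 0.02 | 19 | 0.99 | 0.61-0.69 |
| 0.02 | 28 | 0.99 | 0.66-0.74 |
| 0.10 | 19 | 0.82 | 0.32-0.34 |
| 0.10 | 28 | 0.91 | 0.40-0.43 |

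Example, ICC 0.10, K = 19, ρ = 0.7: m = 21.05, SE = √(0.92 × [0.10 + (0.60 + 0.15)/21.05]/19) = 0.081. Then 0.12/0.081 = 1.48 and power is 0.32.

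**6. Cluster-by-visit variation in a two-visit model.** Let this variance be a fraction f of v at each visit. If it is left out, the variance of the SPIRIT-by-visit estimate is understated by about 1 + (m−1)f/((1−ρ) + f). With m = 400/28 = 14.3, f = 0.02 and ρ = 0.5 this is 1 + 13.3 × 0.02/0.52 = 1.51, and type I error is 2Φ(−1.96/√1.51) = 0.11. For f from 0.01 to 0.04 and ρ from 0.3 to 0.7 it is about 7% to 22%.

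**The case against.** The strongest defence is that 9.4.2 is loosely worded, not wrong. It names 2 weeks as the target, and all four hypotheses in 9.1 are at 2 weeks. Step 1 shows that the continuous power rows fit a single-timepoint comparison. The list of fixed effects need not be closed. Section 2.2 reports that the investigators' earlier trial adjusted for time and baseline values, and the cohort supplement lists time and time by group. The team may well fit something sensible.

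Much of this stands, and it rules out three stronger readings that a reader might infer.
- *No random slope can be fitted.* Not so. With two visits, a cluster slope on visit is identified. With one visit, an independent cluster slope on SPIRIT gives arm-specific cluster variances, and a cluster slope on a dyad covariate such as race is possible. None of these is specified, and none supplies the subject-level effects that the sentence calls for.
- *The trial will report half its effect.* The documents do not say that both visits are outcomes, and they do not give the coding of SPIRIT. One half needs a random intercept, equal visit variances and a constant group indicator. If SPIRIT were coded 0 for everyone at baseline, the halving would not arise. Without a visit term, though, change common to both arms could then be partly credited to SPIRIT.
- *The one-visit reading invalidates the tests.* For DCS and DMC the estimate and standard error do not change. For the binary outcomes the likelihood-ratio test does not change. Only the reported conditional odds ratio moves.

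The defence does not show a model that keeps the stated random effects, uses the listed terms and yields the 2-week effect. That the same document names the time terms for the supplement makes their absence from the primary analysis more conspicuous.

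**Conclusion.** The point holds, and 9.4.2 should be corrected before analysis. Its random-effects sentence, taken with its listed terms, does not give an estimable model for the 2-week effect. On one record per dyad the subject-level effects are unidentified; the harm is an undefined model and an arbitrary odds-ratio scale, not a biased test. On two records the SPIRIT coefficient is a weighted average of the baseline and 2-week differences. The 2-week weight is 0.50 in the simplest case and 0.25-0.40 with the uncorrelated dyad slopes examined.

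The power losses in step 5 illustrate the one-half case only. They contain no slope variance and rest on the assumed correlations, equal allocation and a normal approximation. They are not a forecast of this trial's power.

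A separate consequence of the listed terms applies under any reading: with SPIRIT interacting with cluster size and with race/ethnicity, the SPIRIT coefficient refers to the reference categories and is not an overall effect.

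**What to change.** State one primary model in 9.4.2:
- one 2-week record per dyad, with logit or identity link;
- SPIRIT and the design factors as fixed effects, with the baseline value of the outcome as a covariate;
- a random intercept for cluster only, deleting the random slope and all subject-level random effects.

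If both visits are kept as outcomes, add visit and SPIRIT-by-visit, name the 2-week contrast as the effect, and include dyad, cluster and cluster-by-visit random effects. Step 6 shows why the last of these cannot be dropped.

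In either case, define the 2-week SPIRIT effect as a marginal contrast over cluster size and race/ethnicity.

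Carry the wording to 9.4.3 and 9.4.9. The treatment-intensity outcomes in 9.4.9 have one value per deceased patient and no baseline measurement, so the one-record form without a baseline covariate applies there.

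The cost is SAP wording. The recommended model is simpler than the present one, needs no new data, and agrees with the continuous power rows in 9.2.
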